Other groups have begun to look at DTI as a methodology to examine the changes in the brain in children with craniosynostosis, but in older children^{9 11}, this group found that, "Although these patients have a normal fiber organization, increased diffusivity parameters suggest abnormal microstructural tissue properties of the investigated white matter tracts." Thus far, only animal studies demonstrate the effect of the CVR in a rabbit model of craniosynostosis, which suggests enhanced white matter tracts following intra-cranial expansion^{12, (12)} As this is a pilot study, we will plan to recruit our own control subjects, age matched to our test subjects, but also plan to compare them with de-identified publicly, available datasets, i.e., the Baby Connectome project once they are made available.¹³ Our hypothesis is that CVR has a positive effect on white matter tract development and our proposed study seeks to perform the first human study of the relevant patient population.

Study Aims

Aim 1: We will *establish* pilot data to establish a normative curve of white-matter tract development in normal children under 4 years of age using (DTI). Fractional anisotropy (FA) (a main DTI parameter sensitive to white matter integrity) maps will be created to achieve a normative "white matter change curve" with from infancy to pre-school age.

Aim 2: Will *quantify* the change in white matter tract organization after cranial vault remodeling (CVR) surgery in patients with craniosynostosis by analyzing pre- and post-operative DTI data. This experimental cohort will also be examined in comparison to age-matched controls as compiled in Specific Aim #1, pooled with other centers and compared with published data sets of normal babies from the Baby Connectome Project. . The imaging will be repeated at three intervals after surgery leading up to approximately 4 years of age.

Aim 3: Will assess neurodevelopmental test results in craniosynostosis patients and seek to *correlate* these findings with white matter tract changes.

Title: Neurodevelopmental Outcomes in Craniosynostosis Repair
PI: [name]
Site: Arkansas Children's Hospital
Funding: UAMS Intramural Grant

Study Population

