- pre-anesthesia testing (45-minute duration) & pre-operative phlebotomy including, type and screen (2-4ml), complete blood count (CBC) (0.5ml), and possibly basic metabolic panel (0.5ml), and coagulation panel (2-4ml)
- initial neurodevelopmental testing (Bayley and Mullen Scales – 1 hour duration performed by [name]. [name])
- preoperative MRI functional sequences (60 minute duration) (research-related)

2. Surgery Day: Two cohorts:

- endoscopic-assisted group (age range at surgery between 3- and 6-months old) and
- Open cranial vault remodeling group (age range at surgery between 6- and 24-months old).

3. Six (6) to 6-months post-op:

- clinic visit,
- Neurodevelopmental testing (research-related)
- repeat MRI Imaging(60 minute duration) (research-related)

4. Twelve (12-) to 18-months post-op:

- clinic visit,
- Neurodevelopmental testing (may be repeated earlier at 9-15 months if clinically indicated) (research-related)
- Repeat MRI imaging(60 minute duration) (research-related)

5. Pre-school age (4 years old and younger):

- clinic visit
- Neurodevelopmental testing (research-related)
- repeat MRI Imaging(60 minute duration) (research-related)

Risks and Benefits

One potential risk to study participants is the potential for loss of confidentiality. Measures to protect the confidentiality of study participants will be implemented as described in the Data Handling and Recordkeeping section below. Another potential small risk is the additional anesthesia for the research related MRI's both in terms of the subjective experience of the test subjects themselves and risk of administering

Title: Neurodevelopmental Outcomes in Craniosynostosis Repair
PI: [name]
Site: Arkansas Children's Hospital
Funding: UAMS Intramural Grant

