A master key list of study subject identifiers including names, MRNs, and five-digit study IDNs will be maintained on a password protected computer. As this is a study at ACH, we will also be registering test and control subjects into the Clinical Trials Management System. The study subject identifiers will not be linked to the study data. All study subject identifiers in the master list will be destroyed after publication. De-identified study data will be backed up by maintaining a copy on the computer of the principal investigator [name] and co-investigator [name] MBBS, with the original on the ACH password-protected shared drive server. De-identifiable study data will be retained indefinitely.

Regarding the data from other sites, only de-identified, data will be pooled for analysis, ie quantitative data from the DTI analysis and neurodevelopmental results. Each outside site, will be responsible for de-identifying its own data set for pooling with ours. UAMS will be the repository for the data analysis, and the central database we will keep will ONLY contain the 5-digit IDN. Each institution will retain its key for the IDN and corresponding patient identifiers.

The data safety monitor(DSM) will be an appointed clinical team member, ([name], PA) who will NOT be responsible for recruiting patients into the study but rather have the role of communicating with the PI's mentioned above ([name] [name]) and study coordinator about unanticipated problems, deviations from protocols and/or modifications. If an AE or SAE occurs as defined in the section above to any subject in the study, the study coordinator will relay this information to the IRB in the appropriate time frame but also will notify the DSM to make note in routine reports to the IRB on study progress.

Data Analysis

Primary and Secondary Endpoints

- 1) Understand to a previously unreported level of detail the brain function in children with craniosynostosis using DTI-MRI sequences as compared with age-matched controls
- 2) Determine the effect of CVR on brain development in comparing pre and post-operation DTI-MRI sequences at several intervals post-operatively
- 3) Identify the relationship between the brain development changes as seen on DTI with cognitive testing results

Note that from this master group, multiple cohorts will be grouped for analysis, i.e., single suture and multiple suture craniosynostosis, syndromic craniosynostosis. We

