Title: Neurodevelopmental Outcomes in Craniosynostosis Repair
PI: [name]
Site: Arkansas Children's Hospital
Funding: UAMS Intramural Grant

plan to analyze data both for quality control and preliminary analysis every 6 months while the study is on-going.

Statistical Methods

For the complex analysis of large amounts of MRI data on the same patient and comparing with other patients, we plan to employ biostatistical support baseline and demographic characteristics will be summarized by standard descriptive summaries (e.g., means and standard deviations for continuous variables such as age and percentages for categorical variables such as gender).

Data will be presented as frequencies, medians with ranges, or \pm SD, as appropriate. Tests of group differences will include the paired t-test, χ^2 , and z-test, as appropriate. Repeated measures analysis will also be performed to on pre- and post-operative data for the same patient.

DTI parameters will be computed by standard software and will be compared between patients and controls or between different ages using standard statistical methods. Of note, for each MRI session, whether or not the participant was sedated will be a variable including in analysis.

Ethical Considerations

This study will be conducted in accordance with all applicable government regulations and Arkansas Children's Hospital research policies and procedures. This protocol and any amendments will be submitted and approved by the UAMS Institutional Review Board (IRB) to conduct the study.

The formal consent of each caregiver for their child, using the IRB-approved consent form, will be obtained before that subject is submitted to any study procedure. The caregivers of all subjects for this study will be provided a consent form describing this study and providing sufficient information in language suitable for subjects to make an informed decision about their participation in this study. The person obtaining consent will thoroughly explain each element of the document and outline the risks and benefits, alternate treatment(s), and requirements of the study.

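### The first two post-operative scans are timed from surgery and the last by age, so the last scan is not a common post-operative interval and should not be analysed as one

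*Combined protocol and SAP*

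**What the plan says.** All references are to the combined protocol and SAP.

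- **Study Aims, Aim 2:** "The imaging will be repeated at three intervals after surgery leading up to approximately 4 years of age".
- **Data Analysis, Primary and Secondary Endpoints, item 2:** "Determine the effect of CVR on brain development in comparing pre and post-operation DTI-MRI sequences at several intervals post-operatively".
- **Schedule of Imaging and Neurodevelopmental Assessment, items 3 and 4:** the first two follow-up visits are "Six (6) to 6-months post-op" and "Twelve (12-) to 18-months post-op". The upper limit of the first repeats its lower limit, so I take it as 6 months.
- **Same schedule, item 5:** the last visit is "Pre-school age (4 years old and younger". This is an upper age limit with no lower one and no reference to surgery.
- **Same schedule, item 2:** one surgical cohort, operated on at 3 to 6 months of age, has the endoscopic procedure. The other is given as "Open cranial vault remodeling group (age range at surgery between 6- and 24-months old".
- **Statistical Methods:** tests include the paired t-test, and "Repeated measures analysis will also be performed to on pre- and post-operative data for the same patient". The time variable is not named. Sedation is the only variable named for inclusion at each MRI session.

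**The concern.** Aim 2 and endpoint 2 describe all the follow-up scans as intervals after surgery, but only the first two are. The third is fixed by age, so its distance from surgery is whatever remains after subtracting age at operation.

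A paired or repeated-measures analysis that takes the last visit as one post-operative occasion would pool children scanned at very different times after surgery. The child's delay would follow age at surgery, and hence the cohort. An effect that builds with time since surgery would look larger in children operated on early even if the operations worked equally well, and the pooled last-visit estimate would move with the proportion of endoscopic cases. What is at stake is the interpretation of the later part of the post-operative course.

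**Working it through.** The documents give no power or precision figure on this point, so there is nothing to reproduce. The check is interval arithmetic on the schedule.

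**Inputs from the documents.** Age at surgery is 3–6 months (endoscopic) and 6–24 months (open). The last scan is at about 48 months of age or earlier.

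**Assumptions (mine).** Ages at surgery and at the last scan are uniform within their ranges.

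**Step 1: last scan at exactly 48 months.** Time since surgery = 48 − age at surgery.
- Endoscopic: 48 − 6 = 42 to 48 − 3 = 45 months; mean 48 − 4.5 = 43.5.
- Open: 48 − 24 = 24 to 48 − 6 = 42 months; mean 48 − 15 = 33.0.
- The ranges touch only at 42 months. The means differ by 15 − 4.5 = 10.5 months.

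**Step 2: a window for the last scan.** For scans at ages L to U, the endoscopic range is L − 6 to U − 3 and the open range is L − 24 to U − 6. The overlap runs from L − 6 to U − 6, so its width is U − L.

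| Age at last scan (months) | Endoscopic, months post-op | Open, months post-op | Overlap (months) | Endoscopic children inside open range | Open children inside endoscopic range |
|---|---|---|---|---|---|
| 48 exactly | 42–45 | 24–42 | 0 | 0% | 0% |
| 47–49 | 41–46 | 23–43 | 2 | 33% | 6% |
| 42–48 | 36–45 | 18–42 | 6 | 75% | 17% |
| 36–48 | 30–45 | 12–42 | 12 | 87.5% | 33% |

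The shares were simulated under the uniform assumption and agree with direct calculation. For 42–48, for example, an endoscopic child operated on at age S exceeds 42 months post-op with probability (6 − S)/6. This averages 1.5/6 = 25%, leaving 75% inside the open range. The gap between means is 10.5 months in every row, because it depends only on age at surgery.

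A wider window does not make the visit a common interval. With scans at 36–48 months, a child operated on at 24 months could have the last scan 36 − 24 = 12 months post-op, inside the second visit's window.

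**Step 3: dependence on case mix.** If a proportion p of children is endoscopic and the last scan is at 48 months, the pooled mean time since surgery is 33.0 + 10.5p. That is 35.6 months at p = 0.25, 38.3 at p = 0.50 and 40.9 at p = 0.75. The documents do not give p.

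**Step 4: size of distortion.** Suppose both operations have the same effect curve. The endoscopic-to-open ratio of effects, evaluated at the mean times 43.5 and 33.0 months, is:
- linear accrual: 43.5/33.0 = 1.32;
- saturating, 24-month constant: (1 − e^(−43.5/24))/(1 − e^(−33/24)) = 0.837/0.747 = 1.12;
- saturating, 12-month constant: (1 − e^(−43.5/12))/(1 − e^(−33/12)) = 0.973/0.936 = 1.04.

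The documents give no basis for choosing among these curves.

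**Step 5: what an exact age cannot fix.** If every last scan were at one age, time since surgery at that visit would be an exact function of age at surgery. Duration of effect could not then be separated from age at operation within that visit. Tightening the age window therefore reduces overlap rather than curing the problem.

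**The case against.** Several stronger readings are tempting, and the documents do not support them.

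- **That the cohorts never overlap beyond 18 months.** This needs every last scan at exactly 48 months. Aim 2 gives an approximate age and the schedule allows younger children, so some overlap is to be expected.
- **That the plan commits to analysis by visit number.** It does not; the time axis is simply not stated. Statistical Methods mentions comparison between ages, and Aims 1 and 2 use an age-based normative curve and age-matched controls. A last scan set by age suits that comparison. What stands is that endpoint 2 is framed by post-operative interval, and nothing in the plan excludes treating the last visit as one.
- **That a planned endoscopic-versus-open comparison is biased.** The analysis cohorts named under the endpoints are by suture number and syndrome, not surgical approach. The consequence for the plan as written is a pooled estimate that depends on case mix.
- **That the distortion is 32% or more.** The 32% is the linear case only; the saturating curves give 4% and 12%. Comparing the extreme children, 45/24 = 1.88, describes two individuals and is not the bias of any planned estimate.

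It is also fair to say that a fully specified longitudinal model would cover most of this. That is true, but the plan does not specify one, and even a good model would have limited information for separating duration from age at surgery late in follow-up.

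**Conclusion.** The point holds in a limited form. The schedule mixes two clocks, and the last scan is not a post-operative interval in the sense of Aim 2 and endpoint 2. With last scans near age 4, time since surgery runs from about 24 to 45 months, with little or no overlap between cohorts. Overlap grows as scans move earlier, but the means stay about 10.5 months apart under uniform ages. A by-interval analysis would confuse time since surgery with age at surgery and cohort mix. The amount is uncertain: a ratio of about 1.04 to 1.32 between cohorts, all under assumed accrual curves. The 6-month and 12-to-18-month comparisons do not share this fault, since both are timed from surgery in both cohorts. This is an inexpensive improvement to the analysis plan and does not invalidate the study.

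**What to change.** For endpoint 2, amend Statistical Methods as follows:

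1. In the repeated-measures (mixed) model, use actual months since surgery and age at scan as continuous terms in place of visit number, with results shown by surgical cohort. Keep sedation, as already planned.
2. Report post-operative interval effects at 6 and at 12 to 18 months.
3. Report the last scan as an outcome at about age 4, with the distribution of time since surgery given for each cohort.
4. State that a pooled post-operative trend beyond 18 months is only weakly identified.

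No visit changes are needed. Each site's clinical and imaging records should already allow both time variables to be derived. The data-handling section describes the data pooled across sites as DTI quantities and neurodevelopmental results, so months since surgery and age at scan should be added explicitly as de-identified fields. The downside is that the study can make no firm pooled claim about the trajectory after 18 months.

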Context: Craniosynostosis is a common craniofacial abnormality which can be associated with various clinical syndromes. Though it has been established that children with craniosynostosis score lower on certain developmental tests, the effect of craniosynostosis and cranioplasty surgery on the neural circuitry and brain development is less well known or understood.

Objectives: The purpose of this study is to describe the effect of cranial vault remodeling in children with craniosynostosis on white matter tracts with tractography and Diffusion tensor imaging (DTI), functional MRI, and neurodevelopmental tests, before and after surgery as compared to age-matched controls.

Study Design: This will be a prospective study of patients diagnosed with craniosynostosis and who are going to have open or endoscopic cranial vault remodeling (CVR).

Study Measures: The study will measure MRI sequences before and after surgery and at set time intervals to quantify the effect of white matter tract maturity. Parallel to this, neurodevelopmental tests will be administered at these same intervals.

Background and Rationale

Introduction

Craniosynostosis, the premature ossification and fusion of one or more cranial sutures, is a common craniofacial abnormality occurring in 1 of 2,000 live births.^{1 2} Craniosynostosis can lead to increased intra-cranial pressure in between 12-50% of those affected which may have delayed neuro developmental implications.

The crucial neurodevelopment occurs in the first years of life and is most rapidly progressing during the first year of life. Premature closure of the cranial sutures decrease the intracranial volume and space available for the rapidly developing brain. Cranial vault remodeling (CVR) is the current standard of care to mitigate any possible developmental delay secondary to craniosynostosis and also improve the head shape. CVR is a combined surgery between the neurosurgeon who takes off the cranial bone/bones, and the craniofacial surgeon who assists and reconstructs the cranium with absorbable plates and screws.

After surgery, although there is no doubt that there is an improvement in head shape, the craniofacial skeleton and the soft tissues, but there is less data, and virtually no functional imaging information available addressing the effect of CVR surgery on the growing brain.

Title: Neurodevelopmental Outcomes in Craniosynostosis Repair
PI: [name]
Site: Arkansas Children's Hospital
Funding: UAMS Intramural Grant

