This will be a prospective, longitudinal observational study. Prospective subjects will come from those patients seen as they present to the plastic and/or neurosurgery clinics and a diagnosis of craniosynostosis is suspected. Subsequently, if surgery is indicated, these patients will be approached and considered for inclusion the study. Of note, regardless of study participation it is our practice to follow children with CVR annually until the age of skeletal maturity, i.e., between 16-18 years of age. Annual visits may include but are not limited to the clinic exam, imaging, neurodevelopmental testing and or laboratory blood work, all of which are part of the standard of care for children with craniosynostosis.

We estimate that the duration of this study to be completed by December 31, 2030. We intend to include up to 500 subjects diagnosed with craniosynostosis and up to 60 normal control subjects in this study. The normal control subjects will undergo only a single MRI without sedation, using previously published calming techniques ¹³ and a single Bayley and/or Mullen Scales (age appropriate) administered just prior to the MRI. If the child is deemed within normal limits, they can proceed to the MRI imaging.. We plan to recruit normal, age-matched controls with an awarded UAMS Research Scholar Pilot grant. We will recruit control patients from our neurosurgery and plastic surgery clinics. These patients will be chosen amongst healthy children as stated in the inclusion /exclusion criteria. We expect these patients to be mostly patients who are referred to our clinic with abnormal head shapes due to position but does not have craniosynostosis or any related health problems.

Inclusion Criteria

- Up to 500 children, for all subjects, age of initial study entry: one test group between 3-6 months old (endoscopic assisted), and the other 6-24 months of age (open CVR)) once enrolled, children will be included until 4 years of age.
- Diagnosed with craniosynostosis, single or multiple suture
- Babies with craniosynostosis syndrome including but not limited to Pfeiffers, Aperts, Cruozons, Muenkes.

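### Endpoint 2 defines the effect of surgery as a pre-to-post DTI change with no age term, and the planned control curve is not tied to it, so normal maturation can be read as benefit

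*Combined protocol and SAP*

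**What the plan says.** Data Analysis, Primary and Secondary Endpoints, lists three items. The first compares DTI in patients with age-matched controls. The second, the only one about surgery, is to "Determine the effect of CVR on brain development in comparing pre and post-operation DTI-MRI sequences at several intervals post-operatively", with no comparator.

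Statistical Methods says "Tests of group differences will include the paired t-test", alongside chi-square and z-tests, and then: "Repeated measures analysis will also be performed to on pre- and post-operative data for the same patient". A further sentence compares DTI parameters between patients and controls or between ages by unspecified standard methods. Sedation at each session is the only variable that is explicitly to enter the analysis. No alpha, sidedness or power is given.

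On development, the Introduction states: "The crucial neurodevelopment occurs in the first years of life and is most rapidly progressing during the first year of life". The schedule lists an "endoscopic-assisted group (age range at surgery between 3- and 6-months old" and an open group operated on at 6 to 24 months. Scans follow at about 6 months and at 12 to 18 months after surgery, and at a last visit labelled "Pre-school age (4 years old and younger".

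On controls: "The normal control subjects will undergo only a single MRI without sedation". There are 3 per age band, and published data may replace them. The abstract's objective refers to age-matched controls, Aim 1 builds a normative FA curve, and Aim 2 says the surgical cohort will also be compared with those controls, with other centers' data and with a public data set.

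**The concern.** A within-child difference between two scans contains everything that happened between them. At these ages that includes maturation, which the protocol expects to be rapid and which Aim 1 sets out to chart in normal children. If FA rises with age, the difference will be positive whether or not surgery does anything. That is also the direction of the stated hypothesis, that CVR has a positive effect on white matter tracts.

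Visit cannot stand in for age. The first post-operative scan falls at about 3 + 6 = 9 months of age for the youngest patient and 24 + 6 = 30 months for the oldest. Adding patients makes matters worse, because a larger sample estimates the mixture of growth and surgery more precisely. Data are also to be analysed every 6 months, so an unadjusted pre/post result could appear early. At stake is the study's central question.

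**Working it through.** **Is there a figure to reproduce?** No. The documents give no FA slope, SD, alpha or sample-size derivation. The growth rates, SDs, correlation and patient numbers below are assumptions, and the results are illustrations.

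**Inputs from the documents.** Surgery at 3 to 6 months (endoscopic) or 6 to 24 months (open). First post-operative scan at 6 months. Controls scanned once, 3 at each of 19 listed ages: 19 × 3 = 57, against about 60 stated (not material here).

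**Assumed.** True surgical effect zero. FA = B × log(age) + child effect (SD 0.7) + error (SD 0.7). Total SD is √(0.49 + 0.49) = 0.99, so B is in SD units, and the within-child correlation is 0.49/0.98 = 0.5. B = 0.5, 1 or 2. There are 20 endoscopic and 30 open patients, ages uniform within each range. Two-sided alpha 0.05.

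**Step 1: spurious effect.** The expected change per child is B × log((age + 6)/age).
- Endoscopic: the average of log((a + 6)/a) over 3 to 6 months is 0.863.
- Open: the average over 6 to 24 months is 0.372.
- Mix: 0.4 × 0.863 + 0.6 × 0.372 = 0.568.

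The apparent effect is therefore 0.28, 0.57 and 1.14 SD for B = 0.5, 1 and 2.

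**Step 2: false-positive rate of the raw paired test.** The SD of the change is √(2 × 0.49 + B² × 0.072), where 0.072 is the variance of the log-age step across patients.

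| B | Mean change | SD of change | Ratio × √50 | False positives (noncentral t) | Simulation, 150 trials |
|---|---|---|---|---|---|
| 0.5 | 0.28 | 1.00 | 2.01 | 50% | 49% |
| 1 | 0.57 | 1.03 | 3.92 | 97% | 98% |
| 2 | 1.14 | 1.13 | 7.13 | 100% | 100% |

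Placing the pre-operative scan up to a month before surgery gives 61%, 99% and 100%.

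**Step 3: dependence on sample size.** More generally, suppose growth between scans is only 0.2 SD of the within-child change. The paired test is then falsely positive in 14% at n = 20, 28% at n = 50, 51% at n = 100 and 99% at n = 500, the maximum enrolment.

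**Step 4: age-adjusted analysis.** In the Step 2 setting, a mixed model with log age, its square, patient/control group and a post-surgery term rejects in 5%, 2% and 5% of 150 trials, with mean estimates of 0.01, −0.01 and 0.00 SD. A repeat with 200 trials per growth value gave 3 to 9%. With 150 trials the Monte Carlo standard error at 5% is √(0.05 × 0.95/150) = 1.8 points, so these figures are consistent with about 5%.

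**Step 5: can single-scan controls supply the expected change?** Yes. In a separate simulation (1,500 trials per setting, 57 controls, growth of 1, 2 or 4 SD from 3 to 49 months), each child's change was tested against the change predicted by the control curve. With the curve's own error carried through, rejection was 4.5 to 6.3% for n = 20 to 500. With the curve treated as known, it was 6 to 7% at n = 20 but 30 to 34% at n = 500. The curve's uncertainty therefore has to enter the analysis.

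**Step 6: what age adjustment does not cure.**
- If unoperated patients would mature 20% slower or faster than controls (assumed; growth of 4 SD), the test of Step 5 with curve error included still rejects in 13 to 15% at n = 50 and 31 to 33% at n = 500.
- If open and endoscopic patients differ by an assumed 0.5 SD and the mixed model has no term for it, false positives are 8 to 9% at n = 50 and 31 to 33% at n = 500.

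**The case against.** The strongest reply is that pre-to-post change is not the only planned reading. The objective, Aim 1, Aim 2 and a sentence in Statistical Methods all bring in age-matched controls or age comparisons. The repeated-measures model is unspecified, which is not the same as specified without age. The paired t-test is listed for group differences where appropriate, so the rates above belong to the most literal reading. The study is also a self-described pilot, observational and exploratory.

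Much of this stands. A reader might infer that normal growth will be reported as a benefit of surgery, or that the study cannot answer its question. The documents do not support either: the control data are planned, age at scan can be derived, and nothing forbids adjustment. A reader might also infer that single-scan controls leave no control change to subtract. Step 5 shows that a cross-sectional curve can provide the age-expected change.

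What does not stand is that the planned comparisons settle the matter. Endpoint 1 names age-matched controls and Endpoint 2, directly below it, does not. Aim 2 adds the controls as a further examination, and no rule makes the surgical effect a change relative to expected change. Calling the study a pilot does not alter what the stated contrast estimates.

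**Conclusion.** The point holds as a defect in how Endpoint 2 is defined and analysed. Followed as written, the contrast attributes maturation to surgery, in the direction of the hypothesis. Under the assumed growth of 0.5 to 2 SD per log unit of age and 50 patients, the false-positive rate is roughly 50 to 100%, against about 5% with age adjustment. The size depends on those assumptions, and the documents give neither the direction nor the rate of FA change. That misattribution can occur rests only on the protocol's own account of rapid development at these ages.

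A reader might also infer that staggered surgery ages supply a clean contrast, with open-group pre-operative scans serving as unoperated comparators for endoscopic post-operative scans at the same ages. The documents do not support that. The Surgical Component says endoscopic candidates are typically sagittal cases, while the study also enrols multi-suture and syndromic children. Timing follows age at presentation and is not randomised.

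**What to change.** Define Endpoint 2 as the departure from age-expected DTI after CVR, and word it as change in age-adjusted DTI after CVR. Estimate it in one linear mixed model of all patient and control scans, with:
- a smooth function of exact age at scan;
- patient/control group;
- a time-varying post-surgery term, which is the quantity of interest;
- surgical technique, suture or syndrome type, scanner and sedation;
- a random child effect.

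Estimate the control curve jointly with the patient data so that its uncertainty carries through. If published data replace enrolled controls, the same requirement applies.

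State the limits. Surgery timing is not randomised, and no unoperated craniosynostosis group is followed over time. Departure from normal growth therefore cannot be fully separated from the natural course of the disease. Controls are not to be sedated, so sedation is partly confounded with group.

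The cost is rewording the endpoint and Statistical Methods, somewhat more analysis work, and a more modest causal claim. No new scans are needed, provided exact age at each scan is recorded or derived from date of birth.
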